A multicenter feasibility study (NCT03110601) has also been completed in which DTM™ SCS programming approach was evaluated during the required period for trialing SCS therapy. In this acute study, 20 subjects completed a trial with DTM™ SCS and Conventional SCS programming approaches. In terms of back pain relief, the DTM™ SCS programming approach provided a mean of 68% pain relief and the Conventional SCS programming approach provided a mean of 43% pain relief, which translates to DTM™ SCS achieving 25% greater reduction than Conventional SCS. Notably with DTM™ SCS, 80% of subjects experienced 50% or better back pain relief, and 85% of the subjects preferred therapy received through the DTM™ SCS programming approach. The safety results were in line with expectations of previous SCS studies and the adverse events were mostly resolved within a few days with minimal interventions. There was one serious adverse event, epidural abscess, which although uncommon, is well established as a potential risk in SCS trials and was not related to either programming approach. There were no unanticipated adverse events.

The current study is a post-market, open-label, prospective, randomized, controlled multi-center study that will evaluate DTM™ SCS programming with CMM in comparison to CMM alone for chronic back pain sufferers with or without leg pain. This scientifically sound study will provide more information on safety, efficacy and health economic analytics for the DTM™ SCS programming approach.

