### **B.6.6. Test Arm: End of Trial Assessment**

At the end of the Trial Phase, subjects will be assessed for pain intensity under optimal therapy parameters. Anterior-posterior (AP) and lateral X-ray imaging will be done at the end of the Trial Phase. The subject will be assessed for adverse events and medication usage.

Those who have a "successful Trial Phase" (defined as a 50% or greater pain reduction from Baseline in their back pain) will proceed to permanent implantation of the SCS system to evaluate DTM™ SCS therapy, and permanent implantation of the Intellis™ SCS system will be scheduled. A threshold of 50% for the Trial Phase was predetermined as the minimum pain reduction that warrants consideration of a permanent implant and an opportunity to achieve a 50% pain reduction as defined in the Individual Subject Success criterion (see Section B.7.3).

Data from subjects who did not achieve 50% or greater pain reduction in back pain will not receive permanent implantation and will be carried forward toward the primary endpoint. These subjects will have the leads explanted and will exit the study. Following this exit, subjects will be followed by the Investigator at regular intervals, as dictated by standard of care at each site, in order to facilitate pain management. Any additional non-study related monitoring of the subject will be the responsibility of the subject's personal physician, as dictated by reasonable medical care.

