5.2 Analysis Sets

The following analysis sets are defined for analysis:

- Modified Intent to Treat (mITT): All randomized subjects to the test arms who successfully complete the Trial Phase and all successfully randomized subjects to the control arm.
- Intent-to-Treat (ITT): All successfully randomized subjects who met all the enrollment criteria.
- Per-Protocol (PP): All test subjects who received a permanent device implant and all control subjects who contributed their data to the primary and secondary endpoint without any major protocol deviations (that would render their data unevaluable).

The primary analysis of the primary and secondary endpoints will be performed on the mITT population. Supportive analyses will be performed for the Intent-to-Treat and Per-Protocol population.

For secondary endpoint analyses incorporating crossover data (i.e. data gathered in the post 6-month periods), sensitivity analyses will be performed to examine the impact of crossover.

If a supportive analysis set is the same as the mITT set, the results will be the same and will not be regenerated for that supportive analysis set.

Statistical Analysis Plan		Page 8 of 14
Sponsor SGX International	Study EU RCT DTM SCS vs. CMM	Version 3.0

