5.7.1.2 Handling of Missing Data

For subjects in the DTM™ SCS arm who do experience an unsuccessful Trial Phase, also referred to as a **Trial Failure**, results (i.e., VAS back scores) from the Trial Phase will be utilized for the primary endpoint. Specifically, the Trial Phase results of subjects who failed the Trial Phase will be attributed for each time point throughout the study, as if they remained in the study.

Subjects who did not complete the Trial Phase due to withdrawal (e.g., an adverse event experienced during the Trial Phase, physician withdrawal due to non-compliance, withdrawal of consent, etc.), will not be included in the mITT analysis data set.

In the event of missing primary endpoint data among the mITT subjects either randomized to control or DTM™ SCS subjects who did complete the Trial Phase, the primary analysis for the primary endpoint will be conducted using multiple imputation (MI) methodology rather than the methods specified in Section 5.7.1.1. The specified Pearson Chi-square test will be presented for the observed data as a supporting analysis.

For the MI analysis each missing datum is replaced by multiple values in multiple datasets. The imputed datasets are then analyzed and combined for inference. Since the primary efficacy, and secondary efficacy endpoints, are based on the same underlying data of change in VAS, and vary only in the parameterization (continuous VAS vs. dichotomized responder) or value used for the null hypothesis, the same imputed data sets will be used for the analysis of each endpoint. Imputation will be performed separately by treatment group.

Statistical Analysis Plan		Page 10 of 14
Sponsor SGX International	Study EU RCT DTM SCS vs. CMM	Version 3.0

For each imputation model, covariates will include:

- Baseline variables: age (years), gender, number of year(s) since diagnosed with chronic back pain, unilateral versus bilateral pain, back pain VAS
- Follow-up variables: end of trial phase back pain VAS, follow-up back pain VAS (after device activation) from 1 month through 24 months. The imputation models employed will correspond to the hypothesis being tested, for the primary and secondary endpoints through 6 months, the models will use data through 6 months. For secondary endpoints post 6 months, the model will be extended to the relevant time point.

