5.7.2.1 Handling of Missing Data

Since the two secondary endpoints are based on the same underlying VAS data as that for the primary efficacy endpoint, a similar treatment of handling missing data will be applied for the trial phase outcomes. In particular, for subjects who have a successful Trial Phase and planned to receive a permanent implant, VAS data used for the secondary endpoints will correspond to the results observed at the corresponding collection times (i.e. 1 month, 3 months, 6 months, 9 months, 12 months, 18 months, and 24 months). For subjects who do not have a successful Trial Phase (based on subject's pain score), the VAS data for the secondary endpoints will utilize the results from the end of the Trial Phase.

Subjects who were not able to complete the Trial Phase (e.g., an adverse event experienced during the Trial Phase, physician withdrawal due to non-compliance, withdrawal of consent, etc.) will be removed from the mITT analysis data set as no back VAS pain score is available at the End of Trial visit.

In the event of missing secondary endpoint data the primary analysis of the secondary endpoints will be conducted using multiple imputation instead of the methods specified above. The multiple imputed datasets from the primary endpoint analysis will also be used for the analysis of the secondary endpoints as described in Section 5.7.1.2. The same methods will be used for the responder endpoint evaluation at 1, 3, 9, and 12 months. The evaluation of mean change in VAS at 6 months will estimate the mean change and difference in means between groups along with the associated standard errors which will then be combined across imputations. The imputation model will be extended as needed for the evaluation of the secondary endpoint at 9, 12, 18, and 24 months.

As an additional supporting analysis, likelihood based repeated measures models will be used to produce estimates for the secondary endpoints in the presence of missing data.

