5.9 Safety Analyses

Safety will be assessed by characterizing adverse events at all study visits with descriptive statistics.

All Adverse Events assessed/determined to be study-related study will document seriousness, severity, treatment/intervention provided, relationship to the device/procedure, and resolution.

Adverse events (AE) will be reported for the mITT set. A sensitivity analysis of AEs based on the ITT set will also be performed. AEs will be tabulated with the number of events and subjects with event for each event type and overall. Rates will be reported as the number of subjects who experience at least one event during the analysis interval out of the total number of subjects with follow-up to the beginning of the analysis interval. Serious adverse events will also be tabulated. The rate of all AEs and SAEs reported in the study will be reported.

All AEs and SAEs will also be summarized by relatedness as described above. Adverse events leading to death or study discontinuation will be provided in listing format.

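### The main adverse event table uses the mITT set, which drops test subjects who leave the Trial Phase because of an adverse event

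*SAP*

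**What the plan says.** SAP 5.9 makes mITT the main set for safety: "Adverse events (AE) will be reported for the mITT set". An ITT version is planned as a sensitivity analysis, and "Adverse events leading to death or study discontinuation will be provided in listing format". SAP 5.9 also promises a rate of all events reported in the study, but names no analysis set for it. No separate safety or as-treated set is defined.

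On the test side, SAP 5.2 limits mITT to "All randomized subjects to the test arms who successfully complete the Trial Phase"; on the control side it takes everyone successfully randomized. SAP 5.7.1.2 excludes "Subjects who did not complete the Trial Phase due to withdrawal (e.g., an adverse event experienced during the Trial Phase", among other reasons. SAP 5.7.2.1 repeats the rule and explains it: such subjects "will be removed from the mITT analysis data set as no back VAS pain score is available at the End of Trial visit". For subjects who finish the trial without success, SAP 5.7.1.2 says that "the Trial Phase results of subjects who failed the Trial Phase will be attributed for each time point throughout the study", which treats them as members of the set.

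On follow-up, Protocol B.6.6 assesses adverse events at the end of the Trial Phase. It then says of subjects with an unsuccessful trial: "These subjects will have the leads explanted and will exit the study". Care after exit is the site's usual pain management. Protocol B.6.16 sends crossovers from CMM through the same steps.

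**The concern.** A missing pain score is a reason to leave someone out of a pain analysis. It says nothing about whether that person's harms should be counted. Because SAP 5.9 borrows the efficacy set, a test subject who is harmed with leads in place and withdraws leaves the main table because of the harm. The loss is one-sided, since no comparable rule removes a control.

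Safety is a stated objective, and Protocol C.1 lists infection, haematoma, cerebrospinal fluid leak and paralysis among the risks of surgery or lead placement. Protocol B.1 reports, for a feasibility study confined to the trialing period: "There was one serious adverse event, epidural abscess, which although uncommon, is well established as a potential risk in SCS trials". Serious harm in this phase is therefore foreseeable, and a main table that omits some of it can understate the event rate of the test strategy.

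A related but separate gap is that, in the readable text, subjects with a failed trial exit once the leads are out, with no specified contact to detect a new infection or haematoma afterwards.

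**Working it through.** **Plan's own figures.** Protocol B.5.5.2 needs 100 completers and allows 33% attrition: 100 / (1 − 0.33) = 149.3, or about 150 randomized, as stated. At 1:1 that is 150 / 2 = 75 per arm. Neither document gives an adverse event rate or a Trial Phase withdrawal rate for this trial, so there is no safety figure to reproduce.

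**Who is in the main table.** Setting the sections side by side:

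| Subject | SAP 5.2 | SAP 5.7.1.2 and 5.7.2.1 | Main AE table |
|---|---|---|---|
| Test, leaves during the Trial Phase because of an AE | out | out | out |
| Test, completes an unsuccessful trial | out | used as if in | unclear |
| Test, successful trial | in | in | in |
| Control, including later crossovers | in | in | in |

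SAP 5.9 does not say which treatment a crossover's stimulation-related events count against.

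**Illustration of the first row.** Let *w* be test subjects who withdraw in the Trial Phase for an AE, and *s* the other test subjects who have such an event. Both are assumptions.

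- All-randomized rate = (*w* + *s*) / 75
- mITT rate = *s* / (75 − *w*), with trial failures kept in

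| *w* | *s* | All randomized | mITT |
|---|---|---|---|
| 1 | 0 | 1/75 = 1.3% | 0/74 = 0% |
| 4 | 0 | 4/75 = 5.3% | 0/71 = 0% |
| 1 | 4 | 5/75 = 6.7% | 4/74 = 5.4% |
| 4 | 4 | 8/75 = 10.7% | 4/71 = 5.6% |

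These are whole-study fractions. SAP 5.9 defines rates per interval, over subjects followed to the start of that interval. Someone who withdraws in the Trial Phase and is no longer followed adds little to later intervals in either set, so the difference falls mainly in the Trial Phase interval.

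**A weak guide to *w*.** The feasibility study had one serious event with 20 trial completers: 1/20 = 5%, exact 95% interval 0.1% to 24.9%. The protocol does not say whether that subject withdrew.

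**Second row: trial failures.** The failure rate is not given separately. At an assumed 5%, 20% or 33% (the last being the planning figure for all attrition after randomization):

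- 75 × 0.05 = 3.75, 75 × 0.20 = 15 and 75 × 0.33 = 24.75 trial failures
- test-arm AE set of about 71, 60 or 50 on the SAP 5.2 wording, and near 75 on the SAP 5.7.1.2 wording

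**Number of post-removal calls.**

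- Test arm: about 4 to 25, from the line above.
- Crossovers: take up to 75 controls, because the 50 per arm in the synopsis is a minimum. With the planned 30% control responder rate, 75 × 0.70 = 52.5 might qualify on pain relief, and 52.5 × 0.33 = 17.3 might fail a trial. The lower limit is 0. Crossover also needs dissatisfaction and Investigator agreement, so the true number should be smaller.
- Total: 3.75 + 0, about 4, up to 24.75 + 17.3 = 42.1, about 42. Elective explants would be extra; their number is not given.

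**The case against.** The strongest reply is that SAP 5.9 largely covers this itself. An ITT table is promised, and SAP 5.2 allows a supportive analysis to be skipped only when its set equals mITT. So whenever a harmed subject is excluded, the ITT table has to appear. Events that led to discontinuation are listed. Safety is descriptive, and study success rests only on the primary effectiveness test. All of this stands, and it limits the point to which table is presented as the main one.

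It does not dispose of the point. The ITT table is labelled a sensitivity analysis, a listing gives no rate, and the rate of all events has no named set. ITT in SAP 5.2 is also confined to subjects who met the enrollment criteria, so an ineligible subject who had leads placed would be missing there too. Promoting ITT as defined is therefore not a complete remedy.

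Two stronger readings are tempting. A reader might infer that Trial Phase harms disappear from the report. The ITT table and the listing show otherwise. A reader might also infer that subjects with a failed trial get no adverse event follow-up. The documents do not support that: events are assessed at the end of the trial, Protocol B.6.21 and B.7.6 follow known events to resolution, B.6.21 implies a withdrawal visit without placing it after lead removal, and the Investigator goes on seeing the subject in usual care. What is missing, in the readable text, is a specified contact to find *new* events after removal. Table 1a is scrambled and the body of Table 1b is absent, so even that cannot be fully checked.

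**Conclusion.** The main point holds on the wording. An efficacy rule decides who enters the main adverse event table, it can remove test subjects because they were harmed, and it applies to one arm only. The place of trial failures in that table is undefined. This should be changed, but it does not touch the primary efficacy conclusion.

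The size of any understatement is unknown. The rates above rest on assumed counts and show direction, not a forecast. The effect would sit mainly in the Trial Phase interval and would be visible to anyone who compares the mITT and ITT tables.

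The absence of a contact after lead removal is a secondary point with lower confidence, because it depends on schedule tables that cannot be read. No number of missed events is claimed.

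**What to change.** **SAP 5.9.** Make the main safety set all randomized subjects, whatever is later found about eligibility and whatever the Trial Phase outcome. Add a table of all subjects who had leads placed, counting crossovers' stimulation-related events from their trial implant and their preceding CMM time under CMM. Keep mITT as supportive. This also settles where trial failures belong.

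**Protocol B.6.6**, including crossover trial failures, **and B.6.20** for elective explants where the subject still agrees to contact. Complete the exit eCRF only after one telephone call, limited to adverse events, at a fixed interval after lead removal. Thirty days is an example for the sponsor to confirm. State that AE and SAE reporting stays open until that call. If the full schedule already contains such a contact, a cross-reference is enough.

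**Cost.** Wording in one SAP section and two protocol sections, a little more tabulation, about 4 to 42 calls on the assumptions above plus any elective explants, exit dates about a month later if 30 days is chosen, and possibly slightly higher reported event rates. No clinic visit is added, and the efficacy analyses and sample size are unchanged.

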5.10 Interim Analyses

In order to monitor data on patient safety and to help ensure accuracy of data collection, administrative analyses may be performed. The results of the analyses will not be widely distributed, and access will be limited to those persons on a “need to know” basis. Administrative analyses will not be used to modify the trial or stop early for potential benefit. As there is no chance of early stopping, the type I error rate is not affected. Limiting changes to the protocol also prevents operational bias due to knowledge of interim results.

5.11 Protocol Deviations

Deviations from the procedures outlined in the CIP will be reported by investigational sites on the CRF. Protocol deviations will be summarized for all deviations and by type with event counts and number of subjects with at least one deviation.

Any changes to planned statistical analyses determined necessary prior to performing the analyses will be documented in an amended Statistical Analysis Plan and approved prior to the analysis when possible. Any other deviations or changes from the planned analyses deemed necessary due to violation

Statistical Analysis Plan		Page 14 of 14
Sponsor SGX International	Study EU RCT DTM SCS vs. CMM	Version 3.0

of critical underlying statistical assumptions, data characteristics, or missing data will be clearly described in the clinical study report with justification and rationale.
